4.1. Study Design and Overview

This is a prospective, randomized, double-blind, placebo-controlled, multicenter, two-arm, parallel-group Phase 3 study comparing the efficacy and safety of xevinapant versus matched placebo, when administered in combination with platinum-based chemotherapy and standard fractionation intensity-modulated radiotherapy (IMRT) in previously untreated patients with LA-SCCHN, suitable for definitive CRT (stage III, IVA, IVB; hypopharynx, larynx and/or HPV-negative OPC).

Once a participant has signed the ICF, an identification number will be assigned to him/her and the study related screening procedures will start. Upon confirmation of eligibility, participants will be enrolled and randomized in a 1:1 ratio, using dynamic allocation to:

• **Arm A:** 3 cycles of xevinapant (200 mg/day from Day 1 to 14, per cycle) + IMRT (70 Gy in 35 fractions over 7 weeks, 2.0 Gy/fraction, 5 days/week) + high-dose cisplatin (100 mg/m² on Day 2, per cycle), followed by 3 cycles of monotherapy of xevinapant (200 mg/day from Day 1 to 14, per cycle).

or

• **Arm B:** 3 cycles of placebo (from Day 1 to 14, per cycle) + IMRT (70 Gy in 35 fractions over 7 weeks, 2.0 Gy/fraction, 5 days/week) + high-dose cisplatin (100 mg/m² on Day 2, per cycle), followed by 3 cycles of monotherapy of placebo (from Day 1 to 14, per cycle).

In case of toxicity after the first cisplatin dosing, participants can be switched to carboplatin (AUC=5 or 4 on Day 2 of each subsequent cycle) depending on the toxicity observed, as per Table 6-1.

The schedule of concurrent administration of xevinapant, chemotherapy and IMRT is presented in Table 1-1 and Table 1-2.

Approximately 1000 participants will be screened in order to randomize approximately 700 adult male and female participants.

Note: Additional Chinese participants from China Mainland will be randomized in a China-specific extension cohort (see Section 13.9 for further details).

The following stratification factors will be considered for the randomization:

- Region: North America vs Western Europe vs Rest of the World.
- Primary tumor site: larynx vs other.
- Lymph node involvement: N0-1 vs N2 vs N3.
- T size: T4 vs other.

The study includes the screening period, the treatment period (combination therapy period followed by the monotherapy period, each consisting of 3 cycles), the progression follow-up period (event-free survival [EFS] follow-up) and the OS follow-up period (see Figure 1-1 and Section 1.3 for study schedules of assessments). Each cycle consists of 3 weeks. Participants will be followed up until 386 OS events are observed for the final analysis or the last on-study participant reaches his/her 60-months post-randomization visit or until premature discontinuation from study (see Section 7.2), whichever occurs first.

It is expected that the total duration of the study will be approximately 82 months (6.8 years), (Figure 4-1).

Special oversight committees will include external Independent Data Monitoring Committee (IDMC), Trial Steering Committee, and Firewall Team. The Firewall Team will be composed of a restricted group of individuals within the Sponsor team who are not directly involved in the study conduct activities.

4.2. Scientific Rationale for Study Design

The target population chosen for the study is of patients for whom a significant benefit from treatment with xevinapant combined with the current standard of care (i.e., cisplatin-based standard CRT) is expected. Patients with unresectable or non-resected LA-SCCHN have the poorest prognosis and predominantly experience locoregional failures.

The primary endpoint of the study is EFS, a widely accepted endpoint in LA-SCCHN studies that was shown to be a surrogate endpoint for OS in studies using CRT, both at the individual and study levels (Michiels et al. 2009; Le Tourneau et al. 2009). OS, a standard assessment of clinical benefit in head and neck patients with cancer, will be followed up for at least 5 years.

In line with the radiosensitizing effect of xevinapant, both the efficacy and safety results of the Phase 2 study (Debio 1143-201B) suggest that xevinapant in combination with CRT result in a LRC and PFS benefit associated with an acceptable safety profile (see Clinical development of xevinapant, an antagonist of IAPs in Section 2.2).

EFS as assessed by Investigators will be used for supportive analysis of the primary endpoint. Randomization is expected to compensate for possible inconsistencies in local assessments, hence minimizing any associated bias.

[figure not shown]
4.3. Justification for Study Treatment Dose and Regimen

Xevinapant

In Phase 1 studies with xevinapant (Debio 1143-101 to Debio 1143-106), different dose levels (from 5 to 900 mg/day) and schedules (D1-5 every 2 weeks, D1-5 Q3W or D1-14 Q3W) of xevinapant were administered, as monotherapy or in combination with chemotherapy only, with CRT or with immunotherapy (please refer to the current version of the Investigator's Brochure for further details on the Phase 1 and 2 studies). Doses up to 900 mg/day of xevinapant administered as monotherapy were tolerated and no MTD has been reached.

Tumor penetration and target engagement (IAP1 degradation) in the tumor was shown in Phase 2 studies Debio 1143-201 and Debio 1143-SCCHN-202. In the blood, target engagement and potential signs of downstream effects have been observed at all tested dose levels (100, 200 and 300 mg/day [Days 1-14 Q3W]). Xevinapant exposures at RP2D of 200 mg/day were not associated with unacceptable toxicities and enabled near-maximal clinical effect in terms of tumor metrics.

Based on the results of these studies, 200 mg was determined to be the MTD and was defined as the RP2D, administered on D1-14 of each 3-week cycle with concomitant CRT.

CCI

The safety profile observed in combination with CRT in the Phase 2 study indicates that even though some toxicities occurred more often in the xevinapant arm (anemia, mucositis, and dysphagia of grade 3 according to National Cancer Institute -Common Terminology Criteria for Adverse Events [NCI-CTCAE], which were manageable and reversible) compared to the placebo arm, the number of grade 4 events reported was similar in both arms. All events resolved to at least grade 1 soon after CRT completion with identical median times to resolution between arms. One grade 5 treatment-emergent adverse event (TEAE) was reported and occurred in the placebo arm.

Platinum-based chemotherapy

While there is currently no unanimous consensus on the optimal cisplatin regimen, the high-dose regimen of 100 mg/m² Q3W for up to 3 cycles delivered concomitantly with IMRT is generally considered the standard (Szturz et al. 2017), and has been widely adopted whenever patients are eligible for it. Hence, this regimen will be used in this study.

In the Debio 1143-201B Phase 2 study, up to 3 cycles of high-dose cisplatin were safely administered concomitantly with standard fractionated IMRT and xevinapant. The median cisplatin dose delivered was equivalent and high in both arms (288 mg/m²). Significantly improved antitumoral activity was observed in the xevinapant + CRT arm over the placebo + CRT arm (Section 2.3.2). Therefore, the same high-dose cisplatin regimen will be used in the present study in combination with xevinapant and as the comparator arm.

Nevertheless, in the current study, participants who will experience decreased estimated glomerular filtration rate (eGFR) (< 60 mL/min/1.73m² using the Chronic Kidney Disease - Epidemiology Collaboration [CKD -EPI] creatinine formula) after the first cisplatin dosing, can be switched to an equivalent carboplatin doses (area under the concentration vs time curve [AUC] 5.0 Q3W). This regimen is widely accepted and was reported to have similar efficacy in a recent study (Wilkins et al. 2013).

IMRT

The anatomy of the head and neck is complex due to multiple elements of the digestive, respiratory, nervous and endocrine systems located sometimes within millimeters of each other. Due to the complexity of this anatomical region, large and multiple target volumes, and proximity to organs at risk, RT in this region is also complex.

In addition, high-dose fractionated RT (60-72 Gy) is necessary to cure patients. Irradiation of critical normal tissue can cause severe discomfort with increased acute and late morbidity (Marta et al. 2014). Newer techniques have been developed over the past 2 decades to improve delivery of RT with 2 aims. Firstly, to avoid critical normal tissue to decrease toxicity (Jellema et al. 2007). Secondly, to administer a dose to the tumor volume high enough in order not to compromise control rates (Ghosh-Laskar et al. 2016). Techniques were therefore developed to shape the radiation beams more closely to the target volumes to spare critical tissues, hence reducing toxicity.

IMRT was implemented in the mid-1990s but only became widespread in the last decade. Closer shaping to the tumor contour is made possible by aiming multiple photon beams from different directions and with adjusted intensities. This allows better sparing of the organs at risk resulting in less acute and late toxicity, especially xerostomia (Ghosh-Laskar et al. 2016). Nutting et al. published the results of the PARSPORT study (a Phase 3 multicenter randomized controlled study) in 2011. They concluded that sparing the parotid glands with IMRT significantly reduced the incidence of xerostomia and led to recovery of saliva secretion, hence improving QoL (Nutting et al. 2011). According to the NCCN/ESMO guidelines, IMRT is now considered the standard of care for treating SCCHN.

5. STUDY POPULATION

Assuming a 30% screening failure rate, approximately 1000 participants will be screened worldwide at approximately 280 sites and will undergo study related screening assessments to randomize approximately 700 participants.

Note: Additional Chinese participants from China Mainland will be randomized in a China-specific extension cohort (see Section 13.9 for further details).

The study population include adult patients with LA-SCCHN (stage III, IVA or IVB) with histologically confirmed diagnosis in at least one of the following sites: oropharynx (HPV-negative), hypopharynx and larynx. Participants should be previously untreated and suitable for definitive CRT as determined by a multidisciplinary oncology team, as is currently standard clinical practice.

This study population will be defined by the inclusion and exclusion criteria below. No protocol waivers will be granted.

Upon confirmation of eligibility, participants will be enrolled and randomized.

5.1. Inclusion Criteria

The following inclusion criteria must be met during screening:

- 1. Willing and able to sign written informed consent prior to study screening.
- 2. Male or female ≥ 18 years of age (or based on the country legal age limit for adults) on day of signing the ICF.
- 3. Eastern Cooperative Oncology Group performance status (ECOG PS) 0 or 1.
- 4. Histologically confirmed diagnosis in previously untreated LA-SCCHN patient (stage III, IVA or IVB according to the American Joint Committee on Cancer [AJCC]/TNM Staging System, 8th Ed.) suitable for definitive CRT, of at least one of the following sites: oropharynx, hypopharynx, and larynx.
 - Note: Archival tumor sample to be provided (except for China), if available.
- 5. Evaluable tumor burden (measurable and/or non-measurable tumor lesions) assessed by computed tomography scan (CT-scan) or magnetic resonance imaging (MRI), based on RECIST v 1.1.

- 6. For OPC patients, primary tumors must be HPV-negative as determined by p16 expression using immunohistochemistry (IHC) (pathological report should be available). For OPC participants, p16 cutoff for determination of HPV status is defined in Section 8.1.2.
 - Note: If the site is not able to perform HPV testing by p16 IHC, it will be evaluated by a central laboratory.
- 6. Able to swallow liquids or has an adequately functioning feeding tube, gastrostomy or jejunostomy in place.
- 7. No hearing loss by clinical assessment or ≤ grade 2 hearing impairment (according to NCI-CTCAE v.5).
- 8. Peripheral neuropathy < grade 2.
- 9. Adequate hematologic, renal, and hepatic function as indicated by:
 - eGFR ≥ 60 mL/min/1.73m² (using the CKD-EPI creatinine formula).
 - Absolute neutrophil count (ANC) ≥ 1 500 cells/µL.
 - Platelets ≥ 100 000 cells/µL.
 - Hemoglobin ≥ 9.0 g/dL (blood transfusions during screening are permitted).
 - Aspartate aminotransferase (AST) and alanine transaminase (ALT) ≤ 3.0 x upper limit of normal (ULN).
 - Total bilirubin ≤ 1.5 × ULN (up to 2.0 × ULN is allowed if the direct bilirubin level is normal and the elevation is limited to indirect bilirubin).
- 10. Women of childbearing potential (according to recommendations of the Clinical Trial Facilitation Group) must have a negative serum pregnancy test at screening and must not be breastfeeding.

Women of childbearing potential must agree to use highly effective contraceptive method(s) (see Section 8.1.3) from ICF signature to 6 months after the last administration of chemotherapy or 3 months after last dose of xevinapant/matched placebo, whichever is the latest.

Non-sterilized males who are sexually active with a female partner of childbearing potential must agree to use condom and spermicide from ICF signature to 6 months after the last administration of chemotherapy or 3 months after the last dose of xevinapant/matched placebo, whichever is the latest. Because male condom and spermicide is not a highly effective contraception method, it is strongly recommended that female partners of a male study participant use highly effective contraceptive method(s) (see Section 8.1.3) throughout this period.

Male participants must refrain from donating sperm during the clinical study and for 6 months after the last administration of chemotherapy or 3 months after the last dose of xevinapant/matched placebo, whichever is the latest. If not done previously, cryopreservation of sperm prior to receiving chemotherapy or xevinapant/matched placebo is advised to male participants with a desire to have children.

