- Total bilirubin ≤ 1.5 × ULN (up to 2.0 × ULN is allowed if the direct bilirubin level is normal and the elevation is limited to indirect bilirubin).

TrilynX

11. Women of childbearing potential (according to recommendations of the Clinical Trial Facilitation Group) must have a negative serum pregnancy test at screening and must not be breastfeeding.

Women of childbearing potential must agree to use highly effective contraceptive method(s) from ICF signature to 6 months after the last administration of chemotherapy or 3 months after last dose of xevinapant /matched placebo, whichever is the latest.

Non-sterilized males who are sexually active with a female partner of childbearing potential must agree to use condom and spermicide from ICF signature to 6 months after the last administration of chemotherapy or 3 months after the last dose of xevinapant /matched placebo, whichever is the latest. Because male condom and spermicide is not a highly effective contraception method, it is strongly recommended that female partners of a male study participant use highly effective contraceptive method(s) (see Section 8.1.3) throughout this period.

Male participants must refrain from donating sperm during the clinical study and for 6 months after the last administration of chemotherapy or 3 months after the last dose of xevinapant /matched placebo, whichever is the latest. If not done previously, cryopreservation of sperm prior to receiving chemotherapy or xevinapant/matched placebo is advised to male participants with a desire to have children.

Exclusion criteria

Meeting any of the following criteria at screening will render a participant ineligible for participation in the study:

- 1. Primary tumor of nasopharynx, paranasal sinuses, nasal, or oral cavity, salivary, thyroid or parathyroid gland pathologies, skin or unknown primary site.
- 2. Metastatic disease (stage IVC as per AJCC/TNM, 8th Ed.).
- 3. Prior definitive or adjuvant RT and/or radical surgery to the head and neck region which may jeopardize the primary tumor irradiation plan, or any other prior SCCHN systemic treatment, including investigational agents.
- 4. Use within 14 days prior to randomization or requirement for ongoing treatment with any drug(s) on the prohibited medication list.
- 5. Treatment with an investigational agent or use of an investigational device within 4 weeks of the first dose of study treatment.

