13.2. Cisplatin Administration

Please consult and follow the instructions provided in your local label.

Preparation

Do not use needles or intravenous sets containing aluminum parts that can come in contact with cisplatin for injection during preparation or administration. Aluminum reacts with cisplatin for injection, causing precipitate formation and a loss of potency.

Cisplatin for injection is a cytotoxic drug. Follow applicable special handling and disposable procedures.

Dilution

For preparation of the infusion solution, it is recommended that the solution be further diluted in 1 to 2 L of a compatible infusion solution with or without 37.5 g of mannitol. Refer to detailed references for specific infusion solution stability and compatibility information.

Administration

Administer cisplatin for injection by slow intravenous infusion.

Warnings and Precautions

Nephrotoxicity

Cisplatin for injection can cause dose-related nephrotoxicity, including acute renal failure that becomes more prolonged and severe with repeated courses of the drug. Renal toxicity typically begins during the second week after a dose of cisplatin for injection. Patients with baseline renal impairment, geriatric patients, patients who are taking other nephrotoxic drugs, or patients who are not well hydrated may be more susceptible to nephrotoxicity.

Ensure adequate hydration before, during, and after cisplatin for injection administration (see Appendix 13.3). Measure serum creatinine, blood urea nitrogen, creatinine clearance, and serum electrolytes including magnesium prior to initiating therapy, and as clinically indicated. Consider magnesium supplementation as clinically needed.

Creatinine, eGFR and electrolytes local measurement must take place 48 hours (±12 hours) after cisplatin administration to avoid or mitigate renal toxicities.

Peripheral Neuropathy

Cisplatin for injection can cause dose-related peripheral neuropathy that becomes more severe with repeated courses of the drug. Neurologic symptoms have been reported to occur after a single dose. Neuropathy can also have a delayed onset from 3 to 8 weeks after the last dose of cisplatin for injection. Manifestations include paresthesias in a stocking-glove distribution, areflexia, and loss of proprioception and vibratory sensation. The neuropathy may progress further even after stopping treatment. Peripheral neuropathy may be irreversible in some patients.

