The development of acute leukemia secondary to the use of cisplatin for injection has been reported. In these reports, cisplatin for injection was generally given in combination with other leukemogenic agents.

Embryo-fetal toxicity

Based on human data, cisplatin for injection can cause fetal harm when administered to a pregnant woman. Advise pregnant women and females of reproductive potential of the potential risk to a fetus. Advise females of reproductive potential to use effective contraception during treatment and for 14 months after the last dose of cisplatin for injection. Advise male participants with female partners of reproductive potential to use effective contraception during treatment and for 11 months after the last dose of cisplatin for injection.

Injection site reactions

Injection site reactions can occur during the administration of cisplatin for injection. Local soft tissue toxicity has been reported following extravasation of cisplatin for injection. Severity of the local tissue toxicity appears to be related to the concentration of the cisplatin for injection solution. Infusion of solutions with a cisplatin for injection concentration greater than 0.5 mg/mL may result in tissue cellulitis, fibrosis, necrosis, pain, edema, and erythema.

Because of the possibility of extravasation, closely monitor the infusion site during drug administration.

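### On the planned schedule, the protocol's contraception commitment ends 8.0 months (women) and 5.0 months (men) before the period its own cisplatin appendix advises

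*Protocol*

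**What the plan says.** The commitment a participant makes to enter the trial appears three times in the protocol.

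- The Synopsis (1.1) asks women of childbearing potential to use "highly effective contraceptive method(s) from ICF signature to 6 months after the last administration of chemotherapy", or to 3 months after the last xevinapant/placebo dose if that is later.
- Section 5.1 repeats this for women: "from ICF signature to 6 months after the last administration of chemotherapy or 3 months after last dose of xevinapant/matched placebo", with the later date applying. Non-sterilized men with a partner of childbearing potential "must agree to use condom and spermicide from ICF signature to 6 months after the last administration of chemotherapy", with the same alternative end date.
- Section 8.1.3 gives the same end date. Its first paragraph asks for highly effective measures from women and from men with such partners. Its second paragraph asks men for condom and spermicide and says that this combination is not highly effective.

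Appendix 13.2 states that "cisplatin for injection can cause fetal harm when administered to a pregnant woman". It tells sites to advise women to "use effective contraception during treatment and for 14 months after the last dose of cisplatin for injection" and men with partners of reproductive potential to "use effective contraception during treatment and for 11 months after the last dose of cisplatin for injection". Section 6.1.2.2 refers sites to this appendix for cisplatin administration. The appendix opens with a deferral: "Please consult and follow the instructions provided in your local label".

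**The concern.** Every participant is meant to receive cisplatin, at least on C1D2, so both texts apply to the same people. One is a condition of entry and the other is advice within a drug-administration appendix. Their end dates are months apart, and no sentence says which governs. A participant who honours the eligibility commitment in full may stop contraception while the same protocol still advises against conception because of embryo-fetal risk.

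The stake is participant safety and clarity for sites. The trial's statistical properties are not involved.

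**Working it through.** The protocol states no figure for the gap, so there is none to reproduce. The check is date arithmetic.

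**Inputs**
- Study days from Table 1-1, with C1D1 as day 1: C1D2 = 2, C2D2 = 23, C3D2 = 44, C6D1 = 106.
- Xevinapant/placebo is taken on days 1 to 14 of six cycles (6.1.2.1), so the last planned dose is C6D14 = 106 + 13 = day 119.
- One month = 30.4375 days (SAP 9.8). So 3 months = 91.3 days, 6 months = 182.6, 11 months = 334.8 and 14 months = 426.1.

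**Formulas**
- Commitment end = max(last chemotherapy + 6 months, last xevinapant + 3 months).
- Advised end = last cisplatin + 14 months (women) or + 11 months (men).
- Gap = (advised end − commitment end) / 30.4375.

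**Planned schedule**
- Chemotherapy limb: 44 + 182.6 = day 226.6.
- Xevinapant limb: 119 + 91.3 = day 210.3.
- The chemotherapy limb is later, so the commitment ends at about day 227 (month 7.4 from C1D1), 6 months after the last cisplatin dose.
- Advised end: 44 + 426.1 = day 470.1 (women, month 15.4); 44 + 334.8 = day 378.8 (men, month 12.4).
- Gap: (470.1 − 226.6) / 30.4375 = 8.0 months (women); (378.8 − 226.6) / 30.4375 = 5.0 months (men).

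**Departures from plan**

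| Scenario | Last cisplatin (day) | Commitment end (day) | Gap, women (months) | Gap, men (months) |
|---|---|---|---|---|
| Carboplatin at C3 only | 23 | 226.6 | 7.3 | 4.3 |
| Carboplatin at C2 and C3 | 2 | 226.6 | 6.6 | 3.6 |
| Two cisplatin doses, no further chemotherapy | 23 | 210.3 | 7.8 | 4.8 |
| One cisplatin dose, no further chemotherapy | 2 | 210.3 | 7.2 | 4.2 |
| Three cisplatin doses, last xevinapant 21 days late | 44 | 231.3 | 7.8 | 4.8 |
| Two cisplatin doses, last xevinapant 21 days late | 23 | 231.3 | 7.2 | 4.2 |
| One cisplatin dose, last xevinapant 21 days late | 2 | 231.3 | 6.5 | 3.5 |

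The first four rows assume that xevinapant is completed on time. The 21-day delay is illustrative. These rows are scenarios and do not bound the gap, because a longer xevinapant delay would shrink it further.

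**Delay needed to close the gap** = advised end − 91.3 − 119.
- One cisplatin dose: 336.8 − 210.3 = about 126 days (men); 428.1 − 210.3 = about 218 days (women).
- Three cisplatin doses: 378.8 − 210.3 = about 168 days (men); 470.1 − 210.3 = about 260 days (women).

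**The case against.** The longer advice is already in the protocol, and Section 6.1.2.2 points to it. The two texts differ in kind: an entry commitment, which for women demands highly effective methods, and counselling on effective contraception. A site can comply with both. A reader might therefore infer that participants are left without protection, or that the protocol orders sites to do incompatible things. The documents support neither reading. What stands is narrower: the commitment is shorter than the advice, and nothing links them.

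Appendix 13.2 also reads like general cisplatin labelling. It discusses ototoxicity in children although the trial enrols adults, and it defers to the local label. A reader might take 14 and 11 months as the proven correct periods and 6 months as an error. The documents do not settle which is right. Deferring to local labels does not resolve the difference either, because the appendix prints its own figures and the trial runs at approximately 280 sites.

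The opening sentence of 9.4.2 limits pregnancy reporting to the 9-month visit, which could suggest that later pregnancies go unrecorded. That reading is too strong. Section 8.1.3 and later text in 9.4.2 carry no such limit. Birth defects and spontaneous miscarriages are handled as SAEs, which Section 9.3 collects to end of study. The 9-month visit also falls after the present commitment ends on the planned schedule.

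**Conclusion.** The inconsistency is real and sits in current text. Its size is 8.0 months (women) and 5.0 months (men) if three cisplatin doses and six xevinapant cycles are given on time. Those figures should not be read as applying to every participant: in the other scenarios tested the gap runs from 6.5 to 7.8 months for women and from 3.5 to 4.8 months for men.

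The practical consequence is uncertain. The consent form was not among the documents, so what participants are told is unknown. The number of participants of childbearing potential, or with such partners, is not given. The point should be corrected as a matter of safety wording. It has no bearing on endpoints, type I error or power.

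**What to change.** 1. In Sections 1.1, 5.1 and 8.1.3, keep the existing commitment for the 6-month/3-month period. Add effective contraception until 14 months (women) or 11 months (men) after the last cisplatin dose. If the sponsor's safety experts can justify a shorter period, amend Appendix 13.2 to match instead.
2. Align the consent wording with whichever period is chosen.
3. While editing 8.1.3, reconcile its first paragraph, which requires highly effective measures of men, with its second paragraph and Section 5.1, which require condom and spermicide.
4. Minor: if the contraception period is extended, bring the 9-month limit in the opening sentence of 9.4.2 into line with the rest of 9.4.2 and with 8.1.3.

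The cost is protocol and consent wording, plus a longer period of effective contraception for the participants concerned. No extra scheduled pregnancy tests are needed, and no analysis changes.
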